**Figure 7.7.2-1: Effective Half Life**

$$Effective\ T - HALF = \frac{\tau \ln(2)}{\ln\left[\frac{AI}{AI - 1}\right]}, \text{ where } \tau \text{ is the length of one dosing interval in hours, } AI > 1.$$

**Summary:**

- Summary statistics will be provided for all parameters listed in Section 4.2.2 by treatment, for each dosing schedule.
- Geometric means and coefficients of variation will be presented for all parameters (including Cmax, AUC(0-T), AUC(0-24), AUC(INF), C24, CLT/F, AI\_AUC, and T-HALFeff except for Tmax). Median, minimum, and maximum will be presented for Tmax.
- Dose proportionality analysis for Cmax, AUC(INF) (single dose only) and AUC(0-24) will be presented by analyte as warranted by completeness of the data.
- Means and standard deviations will be presented for other PK parameters like T-HALF.
- **Figure:**
- Plot of geometric mean Ctrough vs. study day will be presented by dose level for each dose schedule.
- Scatter plot of AUC(INF) vs. dose level in log-log scale by dose schedule and superposed with the regression line from the power model
- Scatter plot of AUC(0-24) vs. dose level in log-log scale by dose schedule and superposed with the regression line from the power model
- Scatter plot of Cmax vs. dose level in log-log scale by dose schedule and superposed with the regression line from the power model
- **Listing:**
- All individual PK parameters will be listed including any exclusions and reasons for exclusion from summaries.

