1.4.4 Clinical Pharmacology and Safety

The current study is a first-in-human study.

At the time of the clinical data cutoff date of 21-Dec-2018, a total of 81 subjects had received at least 1 dose of BMS-986158 in Part 1 of the study under Schedule A, Schedule B or Schedule C. Each subject was administered a single dose of BMS-986158 on Cycle 1 Day 1 (4- to 7-day cycle), and no additional doses were administered until Cycle 2 Day 1. On Cycle 2 Day 1 and each subsequent cycle, subjects in Schedule A received once daily (QD) dosing for 5 consecutive days, followed by a 2-day rest period repeated weekly on a 28-day cycle. Subjects in Schedule B received QD dosing for 14 consecutive days, followed by a 7-day rest period on a 21-day cycle and subjects in Schedule A, a total of 44 subjects have received QD dosing of 0.75 mg

(n=5), 1.25 mg (n=4), 2 mg (n=13), 3 mg (n=10), or 4.5 mg (n=12) BMS-986158. In Schedule B, 8 subjects have received QD dosing of 2 mg (n=4), 3 mg (n=4). In Schedule C, 29 subjects have received QD dosing of 2 mg (n=6), 3 mg (n=12) or 4.5 mg (n=11) BMS-986158. All clinical data are preliminary and subject to change.

As of 21-Dec-2018, a total of 79 subjects (97.5%) experienced at least 1 AE. The most frequent AEs (occurring in \geq 20% of subjects) were diarrhea (49 [60.5%] subjects), nausea (43 [53.1%] subjects), fatigue (41 [50.6%] subjects), decreased appetite (34 [42.0%] subjects), vomiting (34 [42.0%] subjects), thrombocytopenia (32 [39.5%] subjects), dyspnoea (23 [28.4%] subjects), anemia (19 [23.5%] subjects), constipation (19 [23.5%] subjects), and cough (17 [21.0%] subjects). A total of 49 subjects (60.5%) experienced Grade 3 to 4 AEs. Five subjects (6.2%) experienced Grade 5 AEs, all assessed by both Sponsor and investigator to be not related to BMS-986158.

Adverse events evaluated as related to BMS-986158 were experienced by 59 of 81 subjects (72.8%). Thirty-four subjects (42%) experienced diarrhea with none experiencing Grade 3 to 4 diarrhea. Thirty subjects (37%) experienced treatment-related thrombocytopenia including 17 subjects (21.0%) with either Grade 3 or 4 events. Thirteen subjects (16%) were reported to have nausea, including 1 (1.2%) Grade 3 nausea. Other Grade 3 to 4 treatment-related AEs include anemia (3 [3.7%] subjects), vomiting, fatigue, increased bilirubin (2 [2.5%] subjects each), and neutropenia and vertigo (1 [1.2%] subject each). There were no treatment-related AE's of Grade 5 reported.

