## 2 STUDY DESCRIPTION

### 2.1 Study Design

This is a phase 1/2a, open label study to characterize the safety and tolerability of BMS-986158 monotherapy in subjects with advanced solid tumors and hematologic malignancies. The study has two segments Part 1 (Phase 1 study - dose escalation, with Schedules A, B and C enrolling at different dosing schedules) and Part 2 (Initial Expansion including subjects with a limited set of tumor types) (see [Figure 2.1-1](#)). In Part 1 and Part 2, BMS-986158 will be studied as monotherapy.

In Part 1, the continuous dosing Schedule A enrolled first. Each subject in Schedules A, B and C of Part 1 is administered a single dose of BMS-986158 on Cycle 1 Day 1 and no additional doses are administered until Cycle 2 Day 1. For subjects in Schedule A on Cycle 2 Day 1, and on each subsequent cycle, subjects receive QD dosing for 5 consecutive days of each week, followed by a 2-day rest period, on a 28-day cycle. For subjects in Schedule B on Cycle 2 Day 1, and on each subsequent cycle, subjects receive QD dosing for 14 consecutive days, followed by a 7-day rest period, on a 21-day cycle. For subjects in Schedule C on Cycle 2 Day 1, and on each subsequent cycle, subjects receive QD dosing for 7 consecutive days, followed by a 14-day rest period, on a 21-day cycle.

[figure not shown]
In Part 2, Schedule A for BMS-986158 administration has been selected for expansion of the 4.5 mg dose, which will be administered for 2 weeks (10 doses) followed by 3.75 mg for the remainder of the treatment period. Adult and adolescent subjects weighing  $\geq 40$  kg will be

administered a flat dose of BMS-986158. Using Schedule A with a loading period of 2 weeks at 4.5 mg followed by 3.75 mg for the remainder of the treatment period, BMS-986158 will be tested as monotherapy, in a limited set of tumor types (NMC, CRPC, DHL, Non-DC-DLBCL, and TNBC; Initial Expansion).

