**7.7.4 Dose Proportionality**

To assess the dose proportionality, the power model described by Gough et al.

$$PK\ Parameter = A * Dose^\beta$$

will be estimated by the simple linear regression of the natural log of the PK Parameter (Cmax, AUC) on the natural log of Dose:

[figure not shown]
$$E[\log(PK\ Parameter) | Dose] = \alpha + \beta * \log(Dose).$$

A slope (β) equal to 1 would indicate perfect dose proportionality. For each PK parameters (Cmax, AUC), the point estimates and 90% CI of the slopes will be provided.

Plots of individual BMS-986158 PK parameter (Cmax, AUC) values versus dose with fitted regression line on a log-log scale will be presented.

Note that dose proportionality analysis may not be performed if there are too few different dose levels (e.g.  $\leq 2$ ) under some dose schedule.

As MAD studies are neither optimally designed nor powered to confirm the presence or absence of meaningful departures from dose proportionality, these results should be interpreted with caution. The estimated regression line will be overlaid on the individual points in the corresponding scatter plot. For MAD studies, these dose proportionality assessments can be done for each day of serial PK sampling, but, unless there are differences from one day to another, only the assessments on the last such day will be discussed.

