**Summary:**

ECG measurements will be summarized by treatment and study day, for each dose schedule separately and across dose schedule.

- ECG measurements will be summarized as follows:
  - The frequency distribution of subjects’ maximum recorded post-dose QTcF, PR, QRS,  $\Delta$ QTcF will be summarized and tabulated for the following ranges:
    - ◆ For QTcF:  $QTcF \leq 450$  msec,  $450 \text{ msec} < QTcF \leq 480$  msec,  $480 \text{ msec} < QTcF \leq 500$  msec,  $QTcF > 500$  msec
    - ◆ For PR:  $PR \leq 200$  msec,  $PR > 200$  msec
    - ◆ For QRS:  $QRS \leq 120$  msec,  $QRS > 120$  msec
    - ◆ For  $\Delta$ QTcF:  $\Delta$ QTcF  $\leq 30$  msec,  $30 \text{ msec} < \Delta$ QTcF  $\leq 60$  msec,  $\Delta$ QTcF  $> 60$  msec
  - The frequency distribution of subjects’ maximum recorded post-dose HR and  $\Delta$ HR and of minimum recorded post-dose HR and  $\Delta$ HR will be summarized and tabulated for the following ranges:
    - ◆ HR and  $\Delta$ HR: HR Value  $> 100$  bpm with  $\Delta$ HR  $> 30$  bpm or
    - ◆ HR value  $< 55$  bpm with  $\Delta$ HR  $< -15$  bpm
  - Summary statistics (n, mean, standard deviation, median, minimum, and maximum) will be presented for each ECG parameter and the corresponding changes from baseline by treatment and time point.
  - Linear mixed effects regression model of  $\Delta$ QTcF vs. BMS-986158 will be provided across dose schedules at Cycle 1 Day 1 (single dose), and may also be provided separately by dose schedule at steady state. The same model will be repeated on the active metabolite plasma concentrations if the latter is sufficiently measured
    - ◆ The plot of  $\Delta$ QTcF versus drug concentrations will include the estimated linear regression taken from the results of fitting a mixed effect model, if available. Mixed effect model with random intercept and slope will be used to explore the relationship between the  $\Delta$ QTcF and plasma concentration data. The following SAS® code is recommended.

```
proc mixed data=Data Set Name method=reml;  
  class usubjid;  
  model  $\Delta$ QTcF =concentration/solution cl alpha=0.10 ddfm=kenwardroger;  
  random intercept concentration/subject=usubjid type=un;
```

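### Single-dose dose proportionality is laid out by schedule although Cycle 1 Day 1 dosing is the same in all three; a common-slope model with schedule intercepts would be tighter at little cost

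*SAP*

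**What the plan says.** SAP 2.1 sets the dosing: "Each subject in Schedules A, B and C of Part 1 is administered a single dose of BMS-986158 on Cycle 1 Day 1", with nothing further until Cycle 2 Day 1. The schedules differ only from Cycle 2 onward.

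SAP 7.7.2 names the parameters: "Dose proportionality analysis for Cmax, AUC(INF) (single dose only) and AUC(0-24) will be presented by analyte as warranted by completeness of the data". Its figure list then has "Scatter plot of AUC(INF) vs. dose level in log-log scale by dose schedule and superposed with the regression line from the power model", and the same by-schedule layout for AUC(0-24) and Cmax.

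SAP 7.7.4 fits a simple linear regression of log parameter on log dose and says that "the point estimates and 90% CI of the slopes will be provided". It adds that the analysis "may not be performed if there are too few different dose levels" under a given schedule, with two or fewer as the example. So the schedule is the unit of analysis.

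SAP 6.2 makes an exception for PK: single-dose results are presented separately for the first week of Cycle 1. It does not say that they are combined across schedules.

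SAP 7.9 does combine them for QTc. The mixed model of ΔQTcF on concentration "will be provided across dose schedules at Cycle 1 Day 1 (single dose"), and by-schedule fits are optional at steady state.

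**The concern.** On Cycle 1 Day 1 a subject given 3 mg has received the same treatment in Schedule A, B or C. The slope of log AUC(INF) on log dose is therefore one quantity. As written, the report would give two or three estimates of it, each from part of the data, and differences among them could be noise. Schedule C, with three dose levels, would have a wide interval. Schedule B, with two, might have no estimate at all.

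Characterising the PK of BMS-986158 is a secondary objective, and this is the planned dose-proportionality evidence after a single dose. What is at stake is the precision and coherence of a descriptive result. The SAP's own handling of QTc at the same visit shows that the alternative fits its logic.

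**Working it through.** **Inputs.** Protocol 1.4.4 gives treated subjects by dose at the 21-Dec-2018 cutoff:

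| Schedule | Dose in mg (n) | N | Levels |
|---|---|---|---|
| A | 0.75 (5), 1.25 (4), 2 (13), 3 (10), 4.5 (12) | 44 | 5 |
| B | 2 (4), 3 (4) | 8 | 2 |
| C | 2 (6), 3 (12), 4.5 (11) | 29 | 3 |

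The counts reproduce the stated total: 44 + 8 + 29 = 81. The documents state no precision for the slope, so there is no planned figure to match. Protocol 1.4.4.1 describes variability only as ranging from low to high, so the CV is an assumption, taken as 30% to 70%.

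**Formulas.** σ = √ln(1 + CV²). Sxx = Σ(ln dose − mean)². The 90% CI half-width is t(0.95, df) × σ/√Sxx. For a common slope with schedule intercepts, Sxx is the sum of the within-schedule values and df = 81 − 4 = 77.

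**Sxx.** A 14.11, B 0.33, C 2.65. Within-schedule total 17.10. Ignoring schedule altogether (fully pooled) 18.89.

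**Half-widths at CV 40%** (σ = √ln 1.16 = 0.385):

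- A: 1.682 × 0.385/√14.11 = 0.172
- B, if fitted: 1.943 × 0.385/√0.33 = 1.31
- C: 1.703 × 0.385/√2.65 = 0.403
- Common slope, schedule intercepts: 1.665 × 0.385/√17.10 = 0.155
- Fully pooled: 1.664 × 0.385/√18.89 = 0.148

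The common-slope interval is 0.155/0.172 = 0.90 of A's width and 0.155/0.403 = 0.38 of C's. σ cancels in these ratios.

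**Range over CV 30% to 70%.**

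| Fit | Half-width |
|---|---|
| A | 0.13–0.28 |
| C | 0.31–0.66 |
| Common slope, schedule intercepts | 0.12–0.25 |
| Fully pooled | 0.11–0.24 |

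**Where the information sits.** As a share of the fully pooled Sxx, A holds 14.11/18.89 = 75% and B holds 0.33/18.89 = 1.7%. Leaving B out of the common-slope model changes the half-width at CV 40% only from 0.155 to 0.157.

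**Why schedule intercepts are needed.** There are two reasons.

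1. Protocol Tables 5.5.1-1 to 5.5.1-3 end Cycle 1 sampling at 72 h in A and C but at 96 h in B. With the 39 h half-life in SAP 1 and a mono-exponential approximation, the share of AUC(INF) beyond the last sample is 2^(−72/39) = 28% against 2^(−96/39) = 18%.
2. The 0.75 and 1.25 mg doses were given only in Schedule A, which enrolled first, so dose is partly confounded with schedule. Mean ln dose is 0.852 in A and 1.110 in B and C together. A level shift d on the log scale between A and the others would move the fully pooled slope by d × (44 × 37/81) × (1.110 − 0.852)/18.89, about 0.27d. An assumed 20% shift (d = ln 1.2 = 0.18, or |ln 0.8| = 0.22) moves it by 0.05 to 0.06. Full pooling gains only 0.172 − 0.148 = 0.024 in half-width over A alone.

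**The case against.** The strongest reply is that little is lost. Schedule A alone carries most of the information, so a reader who wants the best slope largely has it. SAP 7.7.4 itself cautions that studies of this kind are neither designed nor powered to settle dose proportionality. No decision rests on the slope, and the Part 2 dose and schedule are already chosen. All of this stands and sets the weight of the point.

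The text also gives the by-schedule layout some cover. Protocol 8.4.4 asks for plots against dose for each dose regimen. SAP 6.2 sets single-dose PK apart, which makes the schedule wording ambiguous for Cycle 1. SAP 7.7.4 says that, unless days differ, only the last serial sampling day is discussed; for Cmax and AUC(0-24) that day is in Cycle 2. The point therefore bites mainly on AUC(INF). It survives there, because AUC(INF) is analysed after the single dose only and no text provides a joint fit.

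A reader might infer that the schedules can simply be pooled with no downside. The documents do not support that: sampling windows differ, and the lowest doses come from one schedule only. A reader might also infer that the possible loss of Schedule B is a material loss. It is not, at under 2% of the information; the omission is permissive ("Note that dose proportionality analysis may not be performed if there are too few different dose levels"), and further Schedule B dose levels after the cutoff would remove the trigger.

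**Conclusion.** The point holds as an inexpensive improvement. The SAP specifies by-schedule power models for a quantity that arises from identical dosing in all three schedules, and it does not specify a joint fit. A common slope with schedule intercepts gives one estimate whose 90% CI is about 10% narrower than Schedule A's and about 60% narrower than Schedule C's.

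These figures rest on the December 2018 counts of treated subjects, on log-normal variability that is equal across schedules, and on a slope common to the schedules. The absolute widths also rest on the assumed CV; the ratios do not. SAP 6.3 and 7.7 base summaries on PK-evaluable subjects, so actual intervals would be wider if fewer subjects qualify, and the ratios would shift if losses differ by schedule or dose. Nothing here suggests that the by-schedule fits are biased, or that they are unsuitable for Cycle 2, where the regimens do differ.

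**What to change.** Add to SAP 7.7.4: for Cycle 1 Day 1 AUC(INF), and for Cmax and AUC(0-24) where these are assessed on that day, fit one power model across Schedules A, B and C with a common slope and schedule-specific intercepts. Report the slope with its 90% CI, and give the fully pooled fit as a sensitivity check. State that the minimum-dose-levels rule applies to by-schedule fits only. Keep by-schedule fits for the Cycle 2 parameters, and align the AUC(INF) figure in 7.7.2.

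The cost is one extra model per parameter and analyte, and the assumption of a common slope. No new data, visits or samples are needed.

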**7.7.3 Ctrough**

Ctrough values will be listed and summarized by dose and time point. To evaluate the steady state of BMS-986158 concentration in the body, the geometric means of Ctrough vs. cycle will be plotted by dose level for each dose schedule.

**7.7.4 Dose Proportionality**

To assess the dose proportionality, the power model described by Gough et al.

$$PK\ Parameter = A * Dose^\beta$$

will be estimated by the simple linear regression of the natural log of the PK Parameter (Cmax, AUC) on the natural log of Dose:

[figure not shown]
$$E[\log(PK\ Parameter) | Dose] = \alpha + \beta * \log(Dose).$$

A slope (β) equal to 1 would indicate perfect dose proportionality. For each PK parameters (Cmax, AUC), the point estimates and 90% CI of the slopes will be provided.

Plots of individual BMS-986158 PK parameter (Cmax, AUC) values versus dose with fitted regression line on a log-log scale will be presented.

Note that dose proportionality analysis may not be performed if there are too few different dose levels (e.g.  $\leq 2$ ) under some dose schedule.

As MAD studies are neither optimally designed nor powered to confirm the presence or absence of meaningful departures from dose proportionality, these results should be interpreted with caution. The estimated regression line will be overlaid on the individual points in the corresponding scatter plot. For MAD studies, these dose proportionality assessments can be done for each day of serial PK sampling, but, unless there are differences from one day to another, only the assessments on the last such day will be discussed.

## **7.9 Electrocardiogram (ECG)**

All of the available ECG parameter values, single and triplicates, from each participant will be included in the ECG data set. Although all recorded ECG parameter values will be included in the data listings, only ECG parameters with scheduled visits will be included in the summary statistics, graphs, and statistical analysis. Only Part 1 participants will be summarized unless there are more than 5 participants in Part 2.

The triplicate measurements will be averaged at each scheduled measurement timepoints. Baseline values are defined as the average of last recorded triplicate values prior to the first dosing. If triplicate values are not the last recorded values prior to the first dosing, the last recorded value

prior to the first dosing will be used as baseline. For ECG parameters such as QTcF, QT, QTcB, heart rate (HR), QRS, and PR, summary measures (n, mean, standard deviation, median, minimum, and maximum) will be provided.

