≥ Grade 4 hematologic toxicity (neutropenia or thrombocytopenia)	Hold BMS-986158 until returns to baseline or Grade 1.	1st event: Consider reduction by1 dose level.2nd event: Reduce by 1 dose level.		
Grade 3 thrombocytopenia with clinically significant bleeding	Hold BMS-986158 until return to baseline or Grade 1	1st event: Consider reduction by 1 dose level. 2nd event: Reduce by 1 dose level		
≥ Grade 3 non-hematologic AE in subjects receiving maximum medical management.	Hold BMS-986158 until resolves to baseline or Grade 1.	1st event: Consider reduction by 1 dose level.2nd event: Reduce by 1 dose level.		
QTcF > 500 msec confirmed by at least one repeat ECG	Discontinue BMS-986158	Discontinue BMS-986158		
≥ Grade 3 diarrhea not adequately controlled with medication at maximum doses	Hold BMS-986158 until resolves to baseline or Grade 1.	1st event: Consider reduction by 1 dose level.2nd event: Reduce by 1 dose level.		

T 11 4501 . . • . . .

If needed, based on the occurrence of DLTs or other AEs, an individual subject enrolled on any arm may have the BMS-986158 schedule revised to match the alternate schedule on an another arm, at the agreement of the investigator and Sponsor/Medical Monitor, in order to better manage the overall tolerability of study treatment. This schedule change may be in lieu of dose modification shown in Table 4.5.2-1. At the agreement of the investigator and Sponsor/Medical Monitor, subjects who have already had dose reduction may be restarted at the original dose under the revised schedule. For data collection and analysis purposes, all subjects will continue to be classified by the original treatment arm.

Reasons for dose modifications or delays, the supportive measures taken and the outcome must be documented in the subject's chart and recorded in the CRF.

Subjects will be monitored continuously for AEs while on study therapy. Subjects will be instructed to notify their physician immediately for any and all toxicity. The criteria presented in this section for dose modifications and delays are meant as general guidelines.

Assessment of causality (chronology, confounding factors such as disease, concomitant medications, diagnostic tests and previous experience with the agent) must be determined and documented by the investigator, prior to modifying any drugs.

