Table 5.1-3:	0 3	On Treat schedule	eatm Ile	ient (Outli	ne (C	A011	001) -	- Part	1 Es	calati	on - S	chedu	ıle B	- 14 d	ays 01	n / 7 d	On Treatment Outline (CA011001) - Part 1 Escalation - Schedule B - 14 days on / 7 days off dosing schedule
Procedure	Cycle 1 (7 Days)				Cycle 2 (21 Days	cle 2 Days)				5.0	Cycle 3 (21 Days)			Cyc b Cyc	Cycle 4 and beyond (21 days)		EOT ^a	
	I O	1 a 2 a	20	D 4	8 G	D14	510	910	1 0	D 4	D8	D14	810	I O	D8	SI (1		Notes
Clinical Drug Supplies																		
BMS 986158 Administration				Do	sing re	Dosing regimen is 14 days on, 7 days off. Refer to Section 4	is 14 d	lays on	i, 7 day	s off. F	kefer to	Sectic	n 4					Those supplied by BMS or sourced by the investigator.
Abbreviations: $D = Day$; $EOT = End of treatment$;	ay; EOT	= End	of tre	atme	nt;													
^a Refer to Table 5.1-6 for Clinical Follow-up and Survival Follow-up Periods	6 for Cli	nical F	ollow	-up ai	nd Sur	vival F	ollow-	up Per	iods									
^b QTcF assessments ≥450 msec must be confirmed on repeat EC0 matched ECGs will also occur on specific days and time points.	≥450 ms I also occ	ec mus	st be c specif	confirr ic day	med o /s and	n repea time po	t ECG oints.	ECGS	should	d be re	corded	after tl	ie subj	ect has	been s	apine f	or at lea	on repeat ECG. ECGs should be recorded after the subject has been supine for at least 5 minutes. Serial time d time points.

^c ECGs will be collected on C4D8, C6D8 and C8D8. ECGs will not be collected after cycle 8.

d For cycle 10nly, assessments may be performed up to 72 hours prior to dosing.

Contrast enhanced CT of the chest, CT/MRI of the abdomen, pelvis, and all other known and/or suspected sites of disease. See Section 5.3.1 for further details.

- 7 days on/14 days off dosing	
- Schedule C	
t 1 Escalation	
(CA011001)- Par	
On Treatment Outline	
Table 5.1-4:	

]								
		Notes		See Screening notes. Include breast exam if clinically indicated.	C2D14 has a ± 1 day window.	Weight only	See Section 5.3 for details	See Appendix 5 for details
	EOT ^a			Х		Х	Х	Х
	nd 21	DIS			Х	Х		
	cle 4 ai yond (2 days)	D8						
	Cy be	1 0		Х		Х	Х	Х
	ays)	510						
	(21 D	8 G			X	Х	Х	
	Cycle 3 (21 Days)	D¢						
	Cy	1 0		Х		Х	Х	Х
	()	D10						
	Days	L U			Х	Х	Х	
	2 (21	D 4						
schedule	Cycle 2 (21 Days)	D2						
sche	 	1 0			Х	Х	Х	
	Cycle 1(7 Days)	I O		Х		Х	Х	Х
	Procedure		Safety Assessments	Physical Examination (PE)	Targeted Physical Exam	Physical Measurements	Vital Signs	ECOG

- 7 days on/14 days off dosing	
- Schedule C -	

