5.5.1 Pharmacokinetics and Processing

Table 5.5.1-1, Table 5.5.1-2, and Table 5.5.1-3 list the sampling schedules to be followed for the assessment of pharmacokinetics in Part 1. Table 5.5.1-4 lists the sampling schedules to be followed for the assessment of PK for BMS-986158 monotherapy in Part 2 and Table 5.5.1-5 lists the sampling schedules for BMS-986158 and nivolumab combination therapy in Part 2. Further details of blood collection and processing will be provided to the site in the procedure manual.

Table 5.5.1-1:Pharmacokinetic Specimen Collection & ECG Schedule for BMS-
986158 Monotherapy for Schedule A (5 days on / 2 days off) of
Part 1

Study Cycle of Sample Collection (Cycle 1= 7 days, Subsequent cycles are 28 days each)	Study Day of Sample Collection	Event	Time (post BMS-986158 Dose) Hour: Min	BMS-986158 Blood Sample for Plasma Analysis	ECG QTc ^a
1	1	predose	00:00	x ^b	Х
1	1		00:30	Х	
1	1		01:00	Х	

Table 5.5.1-1:Pharmacokinetic Specimen Collection & ECG Schedule for BMS-
986158 Monotherapy for Schedule A (5 days on / 2 days off) of
Part 1

Study Cycle of Sample Collection (Cycle 1= 7 days, Subsequent cycles are 28 days each)	Study Day of Sample Collection	Event	Time (post BMS-986158 Dose) Hour: Min	BMS-986158 Blood Sample for Plasma Analysis	ECG QTc ^a
1	1		02:00	X	Х
1	1		04:00	X	Х
1	1		08:00(±2hr)	X	Х
1	2		24:00 ^c	X	Х
1	3		48:00 ^c	X	
1	4		72:00 ^c	X	
2	1		00:00	X	Х
2	1		00:30	X	
2	1		01:00	X	
2	1		02:00	X	
2	1		04:00	X	
2	1		08:00(±2hr)	X	
2	2		24:00 ^d	X	Х
2	5	predose	00:00	X	Х
2	5		00:30	X	
2	5		01:00	X	
2	5		02:00	X	Х
2	5		04:00	X	Х
2	5		08:00(±2hr)	X	Х
2	6		24:00 ^e	X	Х
2	8	predose	00:00	X	Х
2	8		04:00	X	
4	8 (+3 days) ^f		24:00	X	

^a Triplicate 12-lead ECGs will be collected prior to the first BMS-986158 dose during Cycle 1, Day 1(0 hour), 2 and 4 hours post BMS dose. A single 12 lead ECG will be collected thereafter. The single 12-lead ECG. QTcF assessments ≥450 msec must be confirmed on repeat ECG

- ^c Time represents hours after Cycle 1 Day 1 dose of BMS-986158
- $^{\rm d}$ $\,$ Time represents approximate hours after the Cycle 2 Day 1 dose of BMS-986158 $\,$
- ^e Time represents approximate hours after the Cycle 2 Day 5 dose of BMS-986158
- ^f Sample may be collected at any time from Cycle 4 Day 8 through Cycle 4 Day 11

Table 5.5.1-2:	Pharmacokinetic Specimen Collection & ECG Schedule for BMS-
	986158 - Monotherapy for Schedule B (14 days on/7 days off) of
	Part 1

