8.4.5 ECG Analyses

For subjects with serial ECG measurements and time-matched PK following monotherapy treatment with BMS-986158, changes in the QTcF (Δ QTcF), ECG intervals QRS, and PR, and in heart rate (Δ HR) will be tabulated by treatment and study day. Frequency distributions of max QTcF values, max Δ QTcF, and of max HR in pre-specified categories will be tabulated by treatment. Scatter plots of heart rate, Δ HR, QTc, and Δ QTcF, vs time-matched BMS-986158 concentrations will be provided. A concentration-response effect of BMS-986158 on QTcF may be assessed by a linear mixed effects regression model for Δ QTcF on plasma and serum concentrations, stratified by study day, as well as pooled across days.

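### The scheduled-visit filter in SAP 7.9 also governs the worst-value ECG tables, so an extreme seen only off schedule is tabulated in a lower category

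*SAP*

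**What the plan says.** The opening paragraph of SAP 7.9 separates listings from everything else. For listings, "all recorded ECG parameter values will be included in the data listings". For the rest, "only ECG parameters with scheduled visits will be included in the summary statistics, graphs, and statistical analysis". It adds: "The triplicate measurements will be averaged at each scheduled measurement timepoints".

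The Summary part of 7.9 then calls for a frequency distribution of each subject's "maximum recorded post-dose QTcF, PR, QRS" and change in QTcF. The top QTcF category is above 500 msec, and the top change category is above 60 msec. Maximum and minimum heart rate are handled in a similar table. Nothing there lifts the scheduled-visit restriction.

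The protocol generates ECGs outside the planned time points. In the sampling tables of section 5.5.1, "QTcF assessments ≥450 msec must be confirmed on repeat ECG". Table 4.5.2-1 in section 4.5.2 has an entry for "QTcF > 500 msec confirmed by at least one repeat ECG". For Part 1 Schedule B, a footnote to Table 5.1-3 reads "ECGs will be collected on C4D8, C6D8 and C8D8. ECGs will not be collected after cycle 8", and Table 5.1-4 carries the same footnote for Schedule C. Both tables keep an end-of-treatment ECG.

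Protocol 8.4.5 plans category tables for maximum QTcF and maximum change in QTcF, "and of max HR in pre-specified categories will be tabulated by treatment". That sentence mentions no visit filter.

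**The concern.** A scheduled-visit rule suits means by time point, plots and a concentration–QTcF regression, where each value needs a nominal time. A worst-value table has a different job: it asks how far each subject's ECG ever moved. An unscheduled ECG is typically taken because something prompted it, so these are the recordings least safe to leave out of a maximum.

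The two instructions also conflict. A maximum of what was recorded and a maximum of what was scheduled are different quantities, and two programmers could produce different tables from the same section. The explicit restriction is the more natural one to program.

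This is the only categorical outlier table for ECG intervals in the plan, and the QT effect is a secondary objective. The SAP treats laboratory data differently. Section 7.6 takes post-baseline results up to 30 days after last dose (or all available results for subjects still on treatment), and 7.6.7 uses the worst grade, with no scheduled-visit filter. SAP section 1 says that substantial departures from the protocol's statistical considerations will be identified; 7.9 identifies none here.

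**Working it through.** The plan gives no figure to reproduce. The check is of the text and the logic, followed by an illustration of scale.

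**1. Direction.** Let A be a subject's post-dose ECG values and S the subset from scheduled visits. Then max(S) ≤ max(A) and min(S) ≥ min(A). The filter can move a subject to a less severe category, never to a more severe one.

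**2. When it matters.** Two hypothetical subjects:

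| Subject | Scheduled QTcF (msec) | Repeat | Unscheduled | Max, scheduled only | Max, all ECGs |
|---|---|---|---|---|---|
| 1 | 468, 492, 498 | 507 | 512 | 498 (row >480 to 500) | 512 (row >500) |
| 2 | 505 | 508 | none | 505 (row >500) | 508 (row >500) |

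Subject 1 is misclassified and subject 2 is not. Misclassification requires that no scheduled ECG reaches the subject's true highest category.

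**3. Where scheduled coverage is thin.** In Part 1 Schedule A an ECG is planned on Day 1 of Cycle 4 and beyond and at end of treatment (Table 5.1-2). In Part 2 it is planned on Day 1 of every cycle and at end of treatment (Table 5.1-5). In Schedules B and C, Cycle 1 is 7 days and later cycles are 21 days, so Cycle 8 ends at 7 + 7 × 21 = 154 days, or 22 weeks. After that only the end-of-treatment ECG remains, although Tables 5.1-3 and 5.1-4 make provision for subjects on study for a year or more. A later on-treatment extreme in those schedules could be recorded only on an unscheduled ECG, unless it also shows at end of treatment.

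**4. Scale, assuming exactly one affected subject.** Denominators for Part 1 are from protocol 1.4.4 (data cut 21-Dec-2018); for Part 2, from the planned maximum in SAP 5.2. Exact 95% limits are Beta(0.025; x, n−x+1) and Beta(0.975; x+1, n−x), with a lower limit of 0 when x = 0.

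| Row | n | Scheduled only | All ECGs |
|---|---|---|---|
| 4.5 mg, Schedule A | 12 | 0/12 (0%, 0 to 26.5) | 1/12 (8.3%, 0.2 to 38.5) |
| 4.5 mg, Schedule C | 11 | 0/11 (0%, 0 to 28.5) | 1/11 (9.1%, 0.2 to 41.3) |
| All Schedule A | 44 | 0/44 (0%, 0 to 8.0) | 1/44 (2.3%, 0.1 to 12.0) |
| All Part 1 treated | 81 | 0/81 (0%, 0 to 4.5) | 1/81 (1.2%, 0.0 to 6.7) |
| Part 2 Initial, full enrolment | 45 | 0/45 (0%) | 1/45 (2.2%) |

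The ECG tables are by treatment and study day, within and across dose schedules, so the Part 2 denominator is the single regimen, not a tumor cohort of up to 9. SAP 7.9 summarises Part 2 ECGs only if there are more than 5 participants. The plan asks for no confidence intervals on these counts; they are shown only to indicate how little data each row holds.

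**The case against.** The strongest reply is that little would be hidden. All values and all ECG abnormalities are listed. Protocol 6.7 requires significant ECG worsening to be recorded as an adverse event, and SAP 7.6.3 tabulates and lists events leading to discontinuation. A subject withdrawn for QTcF prolongation should therefore appear in summary tables elsewhere in the report. That stands, and it lowers the severity. It does not make the ECG table right: an empty row above 500 msec could sit beside a QTcF-related discontinuation in the same report.

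A second reply is that the QT objective concerns dose-response and exposure-response, which the concentration–QTcF model addresses, and that protocol 8.4.5 is framed around subjects with serial ECGs and matched PK. This explains the filter for the model. It does not justify it for a maximum.

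A third is that a maximum over all ECGs lets in isolated single readings that a repeat did not confirm, and mixes them with averaged triplicates. The point is fair and calls for a handling rule. But the scheduled-only table already has both features: it counts an unconfirmed scheduled reading, and in Part 1 triplicates are planned only around the first dose, with single ECGs thereafter.

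A reader might also infer that mandated repeats are all unscheduled and never reach the table. The documents do not say so. The filter is on scheduled visits, and the SAP does not say whether a repeat taken at such a visit qualifies.

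**Conclusion.** The point holds in a limited form. SAP 7.9 applies a by-visit filter to worst-value tables and contradicts its own description of them. The effect is one-way and falls on subjects whose most extreme category appears only on an unscheduled ECG, or on a repeat not classed as scheduled. The size is unknown: the documents report neither a QTcF above 500 msec nor a count of unscheduled ECGs, so 0/12 versus 1/12 (8.3%) and 0/45 versus 1/45 (2.2%) are illustrations that assume one case.

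Stronger readings are not supported. It would be wrong to conclude that any subject withdrawn for a confirmed QTcF above 500 msec drops out of the top row; one scheduled reading above 500 msec, including at end of treatment, keeps the subject there. It would also be wrong to say that ECG monitoring ends at Cycle 8 in general; that gap is confined to on-treatment ECGs in Part 1 Schedules B and C. With the values retained in listings, adverse event tables as a second route, and no formal hypothesis in this early-phase study, this is a should-fix, not a must-fix.

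**What to change.** Keep the scheduled-visit restriction for by-time-point summaries, plots and the concentration–QTcF model. Add to SAP 7.9 that the maximum and minimum category tables (QTcF, change in QTcF, PR, QRS, heart rate and its change) use all ECGs after first dose, whether scheduled, unscheduled or repeat, up to 30 days after last dose, matching the window already used for laboratory summaries.

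State the handling rule with it: average replicates taken at the same time point, treat every other ECG as a separate record, and flag in the listing whether a QTcF above 500 msec was confirmed on repeat.

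The cost is a short SAP clarification and a changed filter in one program. The table may look slightly less favourable and may include isolated unconfirmed single readings, which the flag lets a reader identify. The rule should be fixed before database lock, since a choice made after the outliers are known would be hard to defend.
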